5.3.2 Infusion Reaction Management Guidelines

Treatment recommendations are provided below and may be modified based on local treatment standards and guidelines as medically appropriate:

Remain at bedside and monitor subject until recovery from symptoms.

5.3.2.1 For Grade 1 symptoms: (Mild reaction; infusion interruption not indicated; intervention not indicated)

Infusion rate may be slowed or interrupted and restarted at 50% of the original infusion rate when symptoms resolve; if no further complications

ensue after 30 minutes, the rate may be increased to 100% of the original infusion rate. Monitor patient closely.

The following prophylactic premedications are recommended for future infusions: diphenhydramine (or equivalent) and/or paracetamol (acetaminophen) at least 30 minutes before additional nivolumab administrations, slowing infusion rate as above.

5.3.2.2 For Grade 2 symptoms: (Moderate reaction requires therapy or infusion interruption but responds promptly to symptomatic treatment [e.g., antihistamines, non-steroidal anti-inflammatory drugs, narcotics, corticosteroids, bronchodilators, IV fluids]; close observation for recurrence and treatment medications may need to be continued for 24-48 hours, and no further nivolumab will be administered at that visit.)

Stop the nivolumab infusion, begin an IV infusion of normal saline, and treat the subject with diphenhydramine and/or paracetamol (acetaminophen); remain at bedside and monitor patient until resolution of symptoms. Corticosteroid or bronchodilator therapy may also be administered as appropriate. If the infusion is interrupted, then restart the infusion at 50% of the original infusion rate when symptoms resolve; if no further complications ensue after 30 minutes, the rate may be increased to 100% of the original infusion rate. Monitor patient closely. If symptoms recur, re-administer diphenhydramine IV, remain at bedside, and monitor the patient until resolution of symptoms. The amount of study drug infused must be recorded on the electronic case report form (eCRF).

The following prophylactic premedications are recommended for future infusions: diphenhydramine (or equivalent) and acetaminophen (or paracetamol) should be administered at least 30 minutes before additional nivolumab administrations. If necessary, corticosteroids (recommended dose of up to 25 mg of IV hydrocortisone or equivalent) may be used.

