***Axitinib dose titration:**

Individual patient dose titration of axitinib (escalation from starting dose) is permitted on protocol therapy, at the discretion of the treating physician, if the following criteria are met for an individual patient:

1. Two consecutive cycles are completed at a given dose without any adverse reactions $>$ Grade 2 (according to the Common Toxicity Criteria for Adverse Events [CTCAE]).
2. The patient is normotensive, and not receiving anti-hypertension medication.

For patients \geq 18 years old, when a dose increase from 5 mg twice daily is recommended, the axitinib dose may be increased by 1 mg/dose twice daily (for example, from 5 mg twice daily to 6 mg twice daily, etc), up to a maximum of 10 mg twice daily. No more than 1 dose titration can occur in each 2-cycle period per the criteria above. Refer to the table in [Section 5.2.1.1](#) for additional detail.

For patients < 18 years old, see [Appendix IV](#) for dose titration nomograms. No more than 1 dose titration can occur in each 2-cycle period per the criteria above. The maximum titration dose is as per the Dose Level 3 table in [Appendix IV](#).

Nivolumab: IV over 30 minutes, or per institutional guidelines

Age	Dose and Days
≥ 18 years old	Either 240 mg/dose on Days 1 and 15 OR 480 mg/dose on Day 1 only
< 18 years old	3 mg/kg/dose (maximum 240 mg/dose) on Days 1 and 15

The risk of infusion reactions with nivolumab is low and no pre-medications are required. Monitoring for infusion reactions should be per institutional guidelines. Please refer to [Section 5.3.2](#) for suggested infusion reaction management guidelines.

Nivolumab will be distributed by the Division of Cancer Treatment and Diagnosis (DCTD), NCI. Do not use commercial supply.

See [Section 5.0 for Dose Modifications based on Toxicities.](#)

Following completion of a cycle, begin next cycle on Day 29 or when criteria to begin cycle are met, whichever occurs later.

4.4 Arm B: Axitinib (For patients enrolled and randomized to Arm B prior to Amendment 2A) Closed to new accrual with Amendment 2A

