5.2.8 Dose Modifications for Cardiac Toxicity:

Patients who experience \geq Grade 3 left ventricular systolic dysfunction must be removed from protocol therapy and referral to a cardiologist is recommended.

5.2.9 Dose Modifications for Diarrhea:

If Grade 3 (> 3 day duration) or Grade 4 therapy-associated diarrhea is experienced by a patient despite maximal use of anti-diarrheal medications the dose of axitinib should be reduced by one dose level for subsequent cycles (see [Section 5.2.1](#)).

5.3 **Dose Modifications for Nivolumab**

Adverse events (both non-serious and serious) associated with nivolumab exposure may represent an immunologic etiology. These adverse events may occur shortly after the first dose or several months after the last dose of treatment. Nivolumab must be withheld for drug-related toxicities and severe or life-threatening AEs as per Table 2 below. Please also refer to [Appendix V](#) for suggested management guidelines. Please note some of the guidelines include references to medications which may not be appropriate for patients < 18 years of age.

Table 2. Dose Modification Guidelines for Nivolumab-Related Adverse Events

Toxicity	Hold Treatment for Grade	Timing for Restarting Treatment	Treatment Discontinuation
Diarrhea/Colitis (age \geq 18 years)	2-3	Toxicity resolves to Grade 0-1	Toxicity does not resolve within 6 weeks of last dose or inability to reduce corticosteroid to 0.15 mg/kg (up to 10 mg) or less of prednisone or equivalent per day within 6 weeks
	4	Permanently discontinue	Permanently discontinue
Diarrhea (age < 18 years)	2-3 if not reversible within 7 days and related to drug	Toxicity resolves to Grade 0-1 (evaluate for colitis)	Toxicity does not resolve within 6 weeks of last dose or inability to reduce corticosteroid to 0.15 mg/kg (up to 10 mg) or less of prednisone or equivalent per day within 6 weeks
	4	Permanently discontinue	Permanently discontinue
AST, ALT, or Increased Bilirubin (age \geq 18 years)	2	Toxicity resolves to Grade 0-1	Toxicity does not resolve within 6 weeks of last dose
	3-4	Permanently discontinue (see exception below) ^a	Permanently discontinue
AST, ALT (age < 18 years)	2-3 if not reversible within 7 days and related to drug	Toxicity resolves to Grade 0-1 (monitor AST/ALT at least twice per week until resolution)	Toxicity does not resolve within 6 weeks of last dose
	4	Permanently discontinue (see exception below) ^a	Permanently discontinue

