Type 1 diabetes mellitus (if new onset) or Hyperglycemia ^b	T1DM or 3-4	Hold nivolumab for new onset Type 1 diabetes mellitus or Grade 3-4 hyperglycemia associated with evidence of beta cell failure For Grade 2 or higher pancreatitis-associated diabetes, a patient will come off protocol therapy.	Resume nivolumab when patients are clinically and metabolically stable For Grade 2 or higher pancreatitis-associated diabetes, a patient will come off protocol therapy.
Hypophysitis	2-4	Toxicity resolves to Grade 0-1. Therapy with nivolumab can be continued while endocrine replacement therapy is instituted.	Toxicity does not resolve within 6 weeks of last dose or inability to reduce corticosteroid to 0.15 mg/kg (up to 10 mg) or less of prednisone or equivalent per day within 6 weeks.
Hyperthyroidism	3	Toxicity resolves to Grade 0-1	Toxicity does not resolve within 6 weeks of last dose or inability to reduce corticosteroid to 0.15 mg/kg (up to 10 mg) or less of prednisone or equivalent per day within 6 weeks.
	4	Permanently discontinue	Permanently discontinue

Toxicity	Hold Treatment for Grade	Timing for Restarting Treatment	Treatment Discontinuation
Hypothyroidism		Therapy with nivolumab can be continued while thyroid replacement therapy is instituted.	Therapy with nivolumab can be continued while thyroid replacement therapy is instituted.
Infusion Reaction	2 ^c	Toxicity resolves to Grade 0-1	Permanently discontinue if toxicity develops despite adequate premedication
	3-4	Permanently discontinue	Permanently discontinue
Cardiac Toxicities (Including CHF, LV systolic dysfunction, Myocarditis, CPK, and troponin)	1	
Hold dose pending evaluation and observation. (*Patients with evidence of myositis without myocarditis may be treated according as "other event")
 
Note: The optimal treatment regimen for immune mediated myocarditis has not been established. Since this toxicity has caused patient deaths, an aggressive approach is recommended. Evaluate for signs and symptoms of CHF, ischemia, arrhythmia or myositis. Obtain history, EKG, CK (for concomitant myositis), CK-MB. Repeat troponin, CK, and EKG within 2-3 days. If troponin and labs normalize may resume therapy. If labs worsen or symptoms develop then treat as below. Hold drug pending evaluation.
	Toxicity does not resolve within 6 weeks of last dose

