	4	Permanently discontinue	Permanently discontinue

NOTE: Permanently discontinue for any severe or Grade 3 (Grade 2 for pneumonitis) drug-related AE that recurs or any life-threatening event.

^a For patients with liver metastasis who begin treatment with Grade 2 AST or ALT, if AST or ALT increases by greater than or equal to 50% relative to baseline and lasts for at least 1 week, then patients must come off protocol therapy.

^b The protocol distinguishes hyperglycemia responsive to insulin support from pancreatitis-associated diabetes. For the former, as long as laboratory abnormalities are addressed with appropriate supportive care, treatment may continue. For Grade 2 or higher pancreatitis-associated diabetes, patients must come off protocol therapy.

^c If symptoms resolve within one hour of stopping drug infusion, the infusion may be restarted at 50% of the original infusion rate (e.g., from 100 mL/hr to 50 mL/hr). Otherwise dosing will be held until symptoms resolve and the subject should be pre-medicated for the next scheduled dose.

^d Patients will come off study drug if steroids are required to treat drug-related pulmonary toxicity, but not if transient steroids are used to treat other pathology, such as an asthma exacerbation, for example.

^e Patients with intolerable or persistent Grade 2 drug-related AE may hold study medication at physician discretion. Permanently discontinue study drug for persistent Grade 2 adverse reactions for which treatment with study drug has been held, that do not recover to Grade 0-1 within 6 weeks of the last dose.

^f Exception: Any Grade 3 or 4 drug-related laboratory abnormality or electrolyte abnormality, that can be managed with electrolyte replacement, hormone replacement, insulin, or that does not require treatment, does not require discontinuation of nivolumab.

5.3.1 Any Grade 2 drug-related uveitis, eye pain, or blurred vision that does not respond to topical therapy and does not improve to Grade 1 severity within the re-treatment period OR requires systemic treatment must go off protocol treatment.

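### Section 5.3.2.2 both bars and directs a same-visit nivolumab restart after a Grade 2 infusion reaction, and should be aligned with Table 2 footnote c (minor)

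*Combined protocol and SAP*

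**What the plan says.** Three texts in Section 5.3 govern whether nivolumab may be resumed after a Grade 2 infusion reaction.

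- **Section 5.3.2.2, opening parenthetical.** After describing a Grade 2 reaction as one that responds promptly to symptomatic treatment, it ends "and no further nivolumab will be administered at that visit". No condition is attached.
- **Section 5.3.2.2, following paragraph.** Staff stop the infusion, give saline and medication, and monitor. If the infusion was interrupted, they are to "then restart the infusion at 50% of the original infusion rate when symptoms resolve". The rate may return to 100% after 30 minutes without further complications. No time limit is given for resolution.
- **Table 2, footnote c, attached to the Grade 2 infusion-reaction row.** "If symptoms resolve within one hour of stopping drug infusion, the infusion may be restarted at 50% of the original infusion rate". If that condition is not met: "Otherwise dosing will be held until symptoms resolve and the subject should be pre-medicated for the next scheduled dose". The row itself adds: "Permanently discontinue if toxicity develops despite adequate premedication".

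The texts differ in status. Section 5.3 introduces the table with "Nivolumab must be withheld for drug-related toxicities and severe or life-threatening AEs as per Table 2 below". Section 5.3.2 is introduced as recommendations that "may be modified based on local treatment standards and guidelines as medically appropriate", and Sections 4.3.3 and 4.5.3 send staff there "for suggested infusion reaction management guidelines". Section 4.1 says to stop the infusion at Grade 2 or above and give supportive care, then refers to Section 5.3. It does not address restarting.

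**The concern.** The nurse or physician who opens 5.3.2.2 during a reaction finds opposite instructions, a few lines apart, on whether to re-expose the patient that day. Sections 4.3.3 and 4.5.3 name 5.3.2 as the place to look, so it is the text most likely to be in hand. Both open arms receive nivolumab, and patients are eligible from 12 months of age.

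Either choice can depart from Table 2. Following the parenthetical withholds the rest of a dose that footnote c would allow. Following the paragraph beneath it can resume the infusion after an interval at which footnote c would hold it. Sites may settle the conflict differently. What is at stake is consistent patient management; no endpoint or analysis depends on it.

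**Working it through.** No arithmetic applies, because the plan states no figure on this point. The check is to apply each text to every timing of symptom resolution.

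| Text | Symptoms clear within one hour | Still Grade 2, clear after one hour but during the visit |
|---|---|---|
| 5.3.2.2 parenthetical | No restart | No restart |
| 5.3.2.2 following paragraph | Restart at 50% | Restart at 50% |
| Table 2 footnote c | May restart at 50% | Hold; premedicate the next scheduled dose |

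1. **Within 5.3.2.2.** The two texts disagree in both columns, so there is no case in which staff can obey both.

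2. **Parenthetical against footnote c.** They disagree in the first column, where the parenthetical is stricter. In the second column both mean no restart at that visit.

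3. **Following paragraph against footnote c.** They share the half-rate restart and the trigger of symptom resolution. In the first column the paragraph directs what footnote c only permits. In the second column they disagree, because the paragraph has no one-hour limit.

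4. **How wide is the second column?** Grade 2 is defined in 5.3.2.2 as promptly responsive. Section 5.3.2.3 classes a prolonged reaction, one slow to respond to medication or to a short pause, as Grade 3 with permanent discontinuation. Many slow-resolving reactions would therefore leave 5.3.2.2 before its restart sentence applied. The protocol does not equate promptly with one hour, so a gap remains for reactions judged promptly responsive that still take more than an hour to clear.

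5. **Could the restart refer to a later visit?** No. The sentence concerns an interrupted infusion, gives a 30-minute step-up, and is followed by a requirement to record the amount infused. Future infusions have a separate paragraph on premedication.

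6. **Could the bar apply only to recurrence?** That may have been the intention, but the text does not say so. The parenthetical describes Grade 2 reactions in general. The recurrence sentence in 5.3.2.2 calls for repeat diphenhydramine and monitoring, without an instruction to stop nivolumab. Section 5.3.2.3 lists symptoms that come back after getting better as Grade 3. A reader of 5.3.2.2 is not told this, which is why a cross-reference is useful.

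**The case against.** The strongest reply is that the protocol already contains a complete rule. Table 2 is mandatory, footnote c covers both outcomes for a Grade 2 reaction, and 5.3.2 is modifiable guidance. On that view this is unaligned wording in advisory text. Much of this stands: footnote c is the sensible working rule, and the acute steps (stop, saline, medication, monitoring) do not conflict. But the protocol states no order of precedence between Table 2 and 5.3.2, Section 4.1 is silent on restarting, and permission to adapt guidance locally does not make self-contradictory guidance usable.

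Three stronger readings are tempting, and the documents do not support them.

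- **A reader might infer that the following paragraph allows a restart at any time.** It does lack the one-hour limit, but the Grade 2 and Grade 3 definitions exclude many slow-resolving reactions from it.
- **A reader might infer that neither 5.3.2.2 text agrees with footnote c at all.** Each agrees in part, as the comparison shows. The accurate statement is that neither matches in full.
- **A reader might try to turn the conflict into a loss of nivolumab exposure.** The documents give no time at which infusions are stopped, allow infusion times other than 30 minutes under institutional guidelines, and tie no endpoint or dose-intensity analysis to the amount infused. Any such figure would rest on invented inputs.

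**Conclusion.** The inconsistency is real and is wrong as written. It is a drafting fault in a safety instruction and does not call any design choice into question. Its size is minor. Section 4.1 calls infusion reactions rare, and Sections 4.3.3 and 4.5.3 call the risk low. No Grade 2 rate is given, so I put no count on the patients affected beyond expecting few. The definition of PFS, the one-sided alpha of 0.15 and the power for the 22-event analysis do not depend on this text.

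The conclusion that 5.3.2.2 contradicts itself rests only on its wording. The choice of footnote c as the rule to adopt rests on reading the mandatory language of Section 5.3 as outranking the advisory language of 5.3.2. That reading is reasonable, but the protocol does not state it. A reader should not conclude that sites have no workable rule; they have one in Table 2, and 5.3.2.2 does not reflect it.

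**What to change.** Change 5.3.2.2 only. Replace the unconditional bar and the open-ended restart with footnote c's rule:

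- After a Grade 2 reaction, stop the infusion and treat as now described.
- If symptoms clear within one hour of stopping, the infusion may be resumed at half the original rate, with the existing 30-minute step-up.
- If they do not, give no more nivolumab at that visit, hold until symptoms have cleared, and premedicate before the next scheduled dose.

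Add one cross-reference: reactions that are prolonged, or that return after improving, are Grade 3 under 5.3.2.3 and are managed there.

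The cost is a few sentences at the next amendment. Table 2, the grade definitions, the stopping rules, the sample size, the analysis and data collection do not change.

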5.3.2.3 For Grade 3 or Grade 4 symptoms: (Severe reaction)

Grade 3 symptoms: prolonged (i.e., not rapidly responsive to symptomatic medication and/or brief interruption of infusion); recurrence of symptoms following initial improvement; hospitalization indicated for other clinical sequelae (e.g., renal impairment, pulmonary infiltrates).

Grade 4 symptoms: (life threatening; pressor or ventilatory support indicated).

Nivolumab will be permanently discontinued

Immediately discontinue infusion of nivolumab. Begin an IV infusion of normal saline, and bronchodilators, epinephrine 1:1,000 solution for subcutaneous administration or 1:10,000 solution injected slowly for IV administration, and/or diphenhydramine IV with methylprednisolone IV (or equivalent), as needed. Patient should be monitored until the investigator is comfortable that the symptoms will not recur.

Investigators should follow their institutional guidelines for the treatment of anaphylaxis. Remain at bedside and monitor patient until recovery from symptoms.

5.3.3 In the case of late-occurring hypersensitivity symptoms (e.g., appearance of a localized or generalized pruritus within 1 week after treatment), symptomatic treatment may be given (e.g., oral antihistamine, or corticosteroids). Additional treatment may be administered prior to next dose as per guidelines in [Section 5.3.2](#).

Please note that late occurring events, including isolated fever and fatigue, may represent the presentation of systemic inflammation. Please evaluate accordingly.

5.3.4 Any adverse event, laboratory abnormality, or intercurrent illness which, in the judgment of the investigator, presents a substantial clinical risk to the subject with continued study drug dosing should go off protocol treatment.

5.3.5 Dosing interruptions are permitted in the case of medical/surgical events or logistical reasons not related to study therapy (e.g., elective surgery, unrelated medical events, patient vacation, and/or holidays). Subjects must resume protocol therapy within 6 weeks of the scheduled interruption. Nivolumab dosing interruption lasting > 6 weeks will require treatment discontinuation, with the following exception: Dosing interruptions > 6 weeks that occur for non-drug-related reasons may be allowed. The study chair should be notified when treatment is re-initiated in a subject with a dosing interruption lasting > 6 weeks. The reason for interruption should be documented in the patient's study record. If toxicity does not resolve to Grade 0-1 within 6 weeks after last infusion, protocol therapy should be discontinued. Subjects with a laboratory adverse event still at Grade 2 after 6 weeks may continue protocol therapy only if asymptomatic and controlled.

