1.15-1.35	10 mg	5 mg	5 mg
1.36-1.56	11 mg	6 mg	5 mg
1.57-1.77	12 mg	6 mg	6 mg
1.78-1.97	13 mg	7 mg	6 mg
≥ 1.98	14 mg	7 mg	7 mg

APPENDIX V: BRISTOL MYERS SQUIBB NIVOLUMAB TREATMENT GUIDELINES ALGORITHM**Endocrinopathy Management Algorithm**

[figure not shown]
Rule out non-inflammatory causes. If non-inflammatory cause, treat accordingly and continue immuno-oncology (I-O) therapy.
Consider visual field testing, endocrinology consultation, and imaging.

Patients on IV steroids may be switched to an equivalent dose of oral corticosteroids (e.g. prednisone) at start of tapering or earlier, once sustained clinical improvement is observed. Lower bioavailability of oral corticosteroids should be taken into account when switching to the equivalent dose of oral corticosteroids.

GI Adverse Event Management Algorithm

[figure not shown]
Rule out non-inflammatory causes. If non-inflammatory cause is identified, treat accordingly and continue I-O therapy. Opiates/narcotics may mask symptoms of perforation. Infliximab should not be used in cases of perforation or sepsis.

Patients on IV steroids may be switched to an equivalent dose of oral corticosteroids (e.g. prednisone) at start of tapering or earlier, once sustained clinical improvement is observed. Lower bioavailability of oral corticosteroids should be taken into account when switching to the equivalent dose of oral corticosteroids.

Hepatic Adverse Event Management Algorithm

Rule out non-inflammatory causes. If non-inflammatory cause, treat accordingly and continue I-O therapy. Consider imaging for obstruction.

Patients on IV steroids may be switched to an equivalent dose of oral corticosteroids (e.g. prednisone) at start of tapering or earlier, once sustained clinical improvement is observed. Lower bioavailability of oral corticosteroids should be taken into account when switching to the equivalent dose of oral corticosteroids.

[figure not shown]
*I-O therapy may be delayed rather than discontinued if AST/ALT ≤ 8 x ULN and T.bili ≤ 5 x ULN.

**The recommended starting dose for grade 4 hepatitis is 2 mg/kg/day methylprednisolone IV.

Note: The dosing of any medications above are provided for patients ≥ 18 years of age.

Neurological Adverse Event Management Algorithm

[figure not shown]
Rule out non-inflammatory causes. If non-inflammatory cause, treat accordingly and continue I-O therapy.

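### Table 2 and Section 5.3.5 give opposite nivolumab instructions for a held Grade 2 liver-test rise that persists at 6 weeks, and neither is said to govern

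*Combined protocol and SAP*

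**What the plan says.** Section 5.3 introduces Table 2 in mandatory terms: "Nivolumab must be withheld for drug-related toxicities and severe or life-threatening AEs as per Table 2 below". It then points to Appendix V for management guidance that it calls suggested.

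- **Table 2, liver rows, Grade 2.** Treatment is held and may restart at Grade 0-1. The discontinuation column reads "Toxicity does not resolve within 6 weeks of last dose". The adult row covers AST, ALT and bilirubin. The row for patients under 18 covers AST and ALT, for Grade 2-3 drug-related rises that do not reverse within 7 days.
- **Table 2, footnote e (all other drug-related toxicity).** "Permanently discontinue study drug for persistent Grade 2 adverse reactions for which treatment with study drug has been held", where these are reactions "that do not recover to Grade 0-1 within 6 weeks of the last dose".
- **Section 5.3.5.** After a general rule that protocol therapy stops if toxicity is not at Grade 0-1 by 6 weeks, the section ends: "Subjects with a laboratory adverse event still at Grade 2 after 6 weeks may continue protocol therapy only if asymptomatic and controlled".
- **Table 2, adult liver row, Grade 3-4.** "Permanently discontinue (see exception below". The exception is footnote a, which opens "For patients with liver metastasis who begin treatment with Grade 2 AST or ALT, if AST or ALT increases by greater than or equal to". It sets the threshold at a 50% rise over baseline and takes such patients off protocol therapy if the rise lasts at least a week.
- **Appendix V, hepatic algorithm footnote.** "I-O therapy may be delayed rather than discontinued if AST/ALT ≤ 8 x ULN and T.bili ≤ 5 x ULN".

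**The concern.** Permanent stopping for liver toxicity is a safety rule that every site should apply in the same way. Here two parts of the same section give different answers for one clinical situation, and a site cannot tell from the text which to follow. Section 2.2.3 singles out hepatotoxicity when it reviews VEGFR inhibitors combined with PD1 inhibitors, so the situation is foreseeable.

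There is also an analysis consequence. Section 9.3 counts adverse events during protocol therapy and for 100 days after treatment discontinuation. A patient who is stopped and an identical patient who continues are therefore observed for different lengths of time in the arm comparison.

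**Working it through.** The plan states no figure on this point, so the main check sets the passages side by side.

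**1. Grade 2 liver test, nivolumab held, still Grade 2 at 6 weeks, drug-related**
- Table 2: restart needs Grade 0-1, and a value still at Grade 2 has not resolved, so the discontinuation column applies. For a patient under 18, a rise lasting 6 weeks has also passed the 7-day condition.
- Section 5.3.5: the value is a laboratory event still at Grade 2 after 6 weeks, so therapy may continue if there are no symptoms and it is under control.
- Patient, grade and time point are the same, and the instructions are opposite. In Arm C nivolumab is the only drug, so both cannot be followed.

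**2. Other laboratory events, Grade 2, held, not at Grade 0-1 by 6 weeks**
- Footnote e: permanent discontinuation.
- Section 5.3.5: may continue on the same two conditions.
- This is the same opposition, but only where the drug was actually held.

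**3. Adult liver tests, Grade 3-4**
- Table 2: permanent discontinuation. Footnote a, the only cited exception, concerns patients with liver metastasis who start at Grade 2 AST or ALT. It contains no multiple of the ULN.
- Appendix V: delay is possible up to 8 x ULN (AST/ALT) and 5 x ULN (bilirubin).
- These conflict only if Grade 3 begins at or below those ceilings. The documents do not print the cut-offs, so this is an assumption. The contrast that Appendix V draws between delaying and discontinuing supports it.

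**4. Effect on the adverse-event window (illustration)**

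Assumptions: nivolumab every 4 weeks on Day 1, no earlier delays, a decision 42 days after the last dose, and a continuing patient who reaches the 26-cycle cap.
- Continuing: 26 x 28 = 728 days of therapy, so the window ends on day 728 + 100 = 828.
- Stopped with last dose in Cycle k: the window ends on day (k - 1) x 28 + 1 + 42 + 100.

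| Last dose in cycle | Window ends, stopped | Gap to day 828 |
|---|---|---|
| 1 | 1 + 142 = 143 | 685 days |
| 6 | 141 + 142 = 283 | 545 days |
| 12 | 309 + 142 = 451 | 377 days |
| 20 | 533 + 142 = 675 | 153 days |

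The gaps are the largest to be expected under these assumptions, because a continuing patient may stop sooner for another reason.

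**5. How many patients**
- Step 1: the documents give no rate of persistent Grade 2 liver tests, so no number follows.
- Step 3: Section 2.2.3 reports Grade 3-4 ALT elevation in 18% (sunitinib plus nivolumab) and 20% (pazopanib plus nivolumab). With 28 / 2 = 14 patients in Arm A, 0.18 x 14 = 2.5 and 0.20 x 14 = 2.8. That counts every Grade 3-4 ALT event at any age and any height.

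**The case against.** **Section 5.3.5 may simply be a rule followed by its exception.** The general 6-week rule comes first and the laboratory allowance next, and Table 2's 6-week column could be read as restating the general rule. That reading works inside Section 5.3.5. It does not settle Table 2, which is introduced as mandatory, carries its own lettered exceptions, and does not cite this one.

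**A reader might infer that the texts conflict for laboratory toxicity in general.** The documents do not support that. Footnote e applies only where the drug was held, and that hold is at the physician's discretion, so a Grade 2 value that was never held does not meet it. Footnote f, on the same row, does not require stopping for Grade 3-4 laboratory abnormalities that are manageable by replacement or need no treatment. The firm conflict is the liver rows. Beyond them it reaches only held Grade 2 events under footnote e.

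**Appendix V is only suggested guidance beside a mandatory table.** This largely stands. The difference in force suggests that Table 2 prevails, although no sentence says so. The flow chart that the footnote belongs to is not in the text available for review, so the value range to which its asterisk is attached cannot be confirmed.

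**The consequences are limited.** This also stands in part. The triggering liver event occurs on therapy and is counted under either reading. In Arm A, Table 2 governs nivolumab and its liver rows do not say that protocol therapy ends. For Grade 3-4 events, Section 5.2.4 separately removes a patient whose axitinib is delayed by more than 21 days, so some would leave therapy whichever text is used.

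**Conclusion.** The inconsistency is real for a held Grade 2 liver-test elevation still at Grade 2 at 6 weeks (AST or ALT at any age, bilirubin at 18 or over), and for other laboratory events that fall under footnote e. The Appendix V point is a possible second inconsistency for adults and depends on the unprinted grade cut-offs.

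The number of patients affected cannot be derived. A reader might take 2 to 3 of 14 Arm A patients as the expected number for the Appendix V point. At the borrowed rates it is at most an upper bound. Patients under 18 with Grade 3 values are held rather than permanently stopped, values above the Appendix V ceilings raise no conflict, and the rates come from sunitinib and pazopanib combinations. For axitinib with a PD1 inhibitor, Section 2.2.3 reports that the combination was tolerable.

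The shift in the adverse-event window is direct in Arm C. In Arm A it arises only if stopping nivolumab ends protocol therapy, which Section 5.3.5 implies and Table 2 leaves open.

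A reader might also infer that the primary analysis is compromised. The documents do not support that: PFS runs from randomization under intent-to-treat (Section 9.4), and the 22 events, one-sided alpha of 0.15 and 80% power do not depend on this rule. Imaging does move to the Section 7.2 schedule once therapy ends, but the direction varies. Scans on therapy are 8-weekly to Cycle 6, against 3-monthly in the first follow-up year, and 16-weekly after Cycle 12.

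This should be corrected because it is a permanent-stop safety rule that sites can read in two ways.

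**What to change.** Reconcile the Table 2 liver rows and footnote e with the last sentence of Section 5.3.5, so that a held Grade 2 laboratory event persisting at 6 weeks has one instruction, cross-referenced in both places. State whether Table 2 or the Appendix V hepatic footnote governs where they differ. It would help to say in the same text whether stopping nivolumab ends protocol therapy in Arm A, since that fixes the end of the Section 9.3 window. Which clinical rule to adopt is for the sponsor. The cost is amendment wording only, with no change to sample size, analyses or data collection.
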